5.8.3 ECG and Vital signs

Vital signs will be summarized using mean change from baseline tables from baseline (VST01). All data is included in listings (UVSL01).

ECG parameters will similarly be summarized using mean change from baseline by visit (EGT01). Abnormal ECGs will be listed (UEGL01).

VST01/EGT01: Vital Signs Table

Vital Sign Results and Change from Baseline by Visit, <Specific Vital Sign>:
<Specify Population>
Protocol: xxnnnnn

Visit	Group 1 (N=nnn)	
	Value at Visit	Change from Baseline
Baseline		
N	nnn	
Mean (SD)	xx.x (xx.x)	
Median	xx.x	
Min-max	xx.x□xx.x	
Week xx		
n	nnn	nnn
Mean (SD)	xx.x (xx.x)	xx.x (xx.x)
Median	xx.x	xx.x
Min-max	xx.x □xx.x	xx.x□xx.x

UEGL_01: Listing of abnormal ECG

Listing of abnormal ECG: <Specify Patient Population with the Safety Evaluable Population as the default>

Protocol: xxnnnnn

Treatment: XXXX

Center/ Patient ID	Age/Sex/ Race	Study Day	Visit	ECG Result	Heart Rate (BPM)	msec						T Wave	U Wave
						P R	Q R	Q S	QT T	QT cB	QT cF		
[REDACTED]		1	SCREENING	ABNORMAL, NOT CLINICALLY SIGNIFICANT	59	114	118	94	390	400	NORMAL	ABSENT/NORMAL	
		60	WEEK 5	ABNORMAL, NOT CLINICALLY SIGNIFICANT	61	110	108	94	390	400	NORMAL	ABSENT/NORMAL	
		1	WEEK 1	ABNORMAL, NOT CLINICALLY SIGNIFICANT	55	118	108	94	390	407	NORMAL	ABSENT/NORMAL	

UVSL_01: Listing of Vital Signs

Listing of Vital Signs

Protocol: xxnnnnn

Treatment: XXXX

Center/ Patient ID	Age/Sex/ Race	Study Day	Visit	Systolic Blood Pressure [mmHg]	Systolic Blood Pressure [mmHg]	Pulse Rate [BEATS/MIN]	Respiratory Rate [BREATHS/MIN]	Temperature [C]	Weight [kg]
[REDACTED]		-1	SCREENING	xxx	xx	xx	xx	xx.x	xx.x
		60	WEEK 5	xxx	xx	xx	xx	xx.x	xx.x
		1	WEEK 1	xxx	xx	xx	xx	xx.x	xx.x

5.8.4 Laboratory Data

5.8.4.1 General rules of laboratory reporting

The reporting units of laboratory values are SI units. All valid assessments must therefore be converted into SI units.

The categorization is the adapted NCI CTCAE, v4.0 grading. The assessment values are assigned to the categories 1-5 as per the NCI CTCAE, v4.0 Grading definition.

In calculating change from baseline at Visit X, only patients with non-missing values at both baseline and Visit X are included. All available data are, however, used in identifying abnormalities in shift tables.

All laboratory data will be listed. The listing will include NCI CTCAE, v4.0 grades and for the parameters for which WHO grading is not available, values outside of normal ranges are flagged

The laboratory data will be summarized in the following ways:

- 1) Change from baseline
- 2) Shift tables – this method requires the following:
 - a) type of categorization: NCI CTCAE
 - b) Highest NCI-CTCAE Grade Post-Baseline

5.8.4.2 Derived Records

1) Creatinine Clearance

The creatinine clearance will be derived based on the Cockcroft-Gault formula unadjusted and adjusted for body surface area (BSA). Both formulas are given below.

Unadjusted Cockcroft-Gault formula:

$$C_{CR} \left[\frac{ml}{min} \right] = \frac{(140 - Age [years]) \times Weight [kg] \times F}{0.8143 \times Creatinine \left[\frac{umol}{l} \right]}$$

where F=1 for male subjects and F=0.85 for female subjects

BSA-adjusted Cockcroft-Gault formula:

$$C_{CR-adj} \left[\frac{ml}{min} \right] = C_{CR} \left[\frac{ml}{min} \right] \times \frac{1.73 [m^2]}{BSA [m^2]}$$

2) Total Neutrophils

Total Neutrophils are derived as the sum of segmented and band Neutrophils. If one of the parameters is missing, it is assumed to be zero. Following this derivation, if there is more than one result per time point, the latest record will be kept. If more than one result is at the same time, the smallest result is kept. In case the total neutrophils are reported together with the segmented and the bands, no calculation will be done, and the total neutrophils are used.

3) Corrected Calcium

Corrected Calcium is derived using the following formula:

$$CA_{corr} \left[\frac{mmol}{l} \right] = Serum Calcium \left[\frac{mmol}{l} \right] + 0.02 \times \left(40 \left[\frac{g}{l} \right] - Albumin \left[\frac{g}{l} \right] \right)$$

ULBL_01: Listing of <Hematology|Biochemistry> Laboratory Test Results with Abnormality Flags

Listing of Laboratory Test Results with Abnormality Flags: <Analysis Population>

Protocol: xxnnnnn

subpopulation:xxxxx

Lab Test (Unit)	Center / Patient ID	Study Day	Visit	Days since Last Treatment Dose	Result in SI Units	Investigator Range in SI Units	SI Units	WHO Grade/Direction	Reference Range Indicator
Lab Test (<unit>)	xxxx/x xx	xx	xx	xx	xx			x/L	Low/High
Lab Test		189	xx	xx	xx				

Note: Only print WHO Grade if >=1

LBT01: Laboratory Tests Table

Laboratory Test Results and Change from Baseline by Visit, <Specific Lab Test>: <Specify Population>
 Protocol: xxnnnnn

Visit	(N=nnn)	
	Value at Visit	Change from Baseline
Baseline		
N	nnn	
Mean (SD)	xx.x (xx.x)	
Median	xx.x	
Min-max	xx.x-xx.x	
Week 2		
n	nnn	nnn
Mean (SD)	xx.x (xx.x)	xx.x (xx.x)
Median	xx.x	xx.x
Min-max	xx.x-xx.x	xx.x-xx.x

Note: Include all scheduled visits.

LBSHIFT: Laboratory Test Shift Table: Highest NCI-CTCAE Grade Post-Baseline : <Population>

Protocol(s):
 Snapshot Date: <Snapshot date>

Subpopulation: (N=24) Type of Abnormality: HYPO

Shift TO:
 Post Baseline
 WORST Value

Shift FROM:
 Baseline

Parameter (SI Unit)	WHO Grade:	Grade 0	Grade 1	Grade 2	Grade 3	Grade 4	Missing
Total							

Hemoglobin (G/L)							
(4.2%)	11 (45.8%)	Grade 0	10 (41.7%)	0	0	0	1
0		Grade 1	0	0	0	0	0
0		Grade 2	0	0	0	0	0
0		Grade 3	0	0	0	0	0

0	Grade 4	0	0	0	0	0	0
5 (20.8%)	Missing	5 (20.8%)	0	0	0	0	0
(4.2%) 16 (66.7%)	Total	15 (62.5%)	0	0	0	0	1
Neutrophils (10 ⁹ /L)							
(4.2%) 10 (41.7%)	Grade 0	9 (37.5%)	0	0	0	0	1
1 (4.2%)	Grade 1	1 (4.2%)	0	0	0	0	0
0	Grade 2	0	0	0	0	0	0
0	Grade 3	0	0	0	0	0	0
0	Grade 4	0	0	0	0	0	0
5 (20.8%)	Missing	5 (20.8%)	0	0	0	0	0
(4.2%) 16 (66.7%)	Total	15 (62.5%)	0	0	0	0	1

5.8.4.3 *Serology*

Serology listings will be produced

Proportion of patients with tabulated for each serological diagnosis

5.8.4.4 *Urinalysis*

Listings of Urine Analyses will be produced.

Shift table by visit from baseline will also be presented for each test parameter.

5.8.5 *Phlebotomy*

Proportions of patients with Prior Phlebotomy summary and Listings of Prior Phlebotomy will be generated.

AEL01_NOLLT: Adverse Event Preferred Terms and Investigator-Specified Terms Listing

Listing of Preferred Terms and Investigator-Specified Adverse Event Terms: <Analysis Population>

Protocol: xxnnnnn

MedDRA System Organ Class	MedDRA Preferred Term	Investigator-Specified Adverse Event Term	
BLOOD AND LYMPHATIC SYSTEM DISORDERS	ANAEMIA NOS	ANAEMIA ANEMIA	
	LEUCOCYTOSIS NOS	LEUKOCYTOSIS	
	LEUCOPENIA NOS	LEUKOPENIA	
	LYMPHADENOPATHY	NECROTIC LYMPH NODE	
		SWOLLEN GLANDS IN THROAT	
		SWOLLEN THROAT GLANDS	
	FEBRILE NEUTROPENIA	FEBRILE NEUTROPENIA NEUTROPENIC FEVER	
	NEUTROPENIA	NEUTROPENIA	
	CARDIAC DISORDERS	CARDIOMYOPATHY NOS	CARDIOMYOPATHY
		CONGESTIVE (DILATED) CARDIOMYOPATHY	DILATED CARDIOMYOPATHY
ANGINA PECTORIS		ANGINA PECTORIS	
PERICARDIAL HAEMORRHAGE		PROBABLE PERICARDIAL BLEED	
TACHYCARDIA NOS		TACHYCARDIA	

Investigator text for AEs encoded using MedDRA version xx.x.

AEL02_02: Listing of Adverse Events

Listing of Adverse Events: <Specify Patient Population with the Safety
Evaluable Population as the default>

Protocol: xxnnnnn

Population: xxx

Center/Patient ID	Adverse Event MedDRA Preferred Term	Age/Sex/Race	Study Day of Onset	AE Duration in Days	Series	Most Extreme Grade (0)	Relation to Study Drug	Outcome (1)	Treatment for AE	Action Taken with Study Drug (2)	Study Period/ (3)
	ANEMIA NOS		260	1	No	1	Yes	2	No	2	1
	APPETITE DECREASED		270	2	No	2	No	3	No	3	2
	DIARRHEA NOS		188	2	No	1	No	3	No	2	3

Investigator text for AEs encoded using MedDRA version xx.x.

(0) Grade: 1 = mild; 2 = moderate; 3 = severe; 4 = life threatening.

(1) Outcome: 1 = fatal; 2 = not recovered/not resolved;

3 = recovered/resolved; 4 = recovered/resolved with sequelae;

5 = recovering/resolving; 6 = unknown.

(2) Action taken with study drug: 1 = dose increased; 2 = dose not changed;

3 = dose reduced; 4 = drug interrupted; 5 = drug withdrawn; 6 = not

applicable; 7 = unknown.

(3) Study Periods:

1 = before study entry 2 = During study 3 = Follow-up

AEL02_03: Listing of Adverse Events leading to withdrawal

Listing of Adverse Events: <Specify Patient Population with the Safety Evaluable Population as the default>

Protocol: xxnnnnn

Subpopulation{}

Center/ Patient ID	Adverse Event MedDRA Preferred Term	Age/Sex/ Race	Study Day of Onset	AE Dura tion in Days	Most Extre me Grade (0)	Cause d by Study Drug	Outco me (1)	Treat ment for AE	Action Taken with Study Drug (2)	Subject disconti nued from study	Study Period (3)	
[REDACTED]	ANEAMIA NOS		0	1	No	1	Yes	2	No	5	No	1
[REDACTED]	APPETITE DECREASED		91	2	No	2	No	3	No	3	Yes	2
[REDACTED]	DIARRHEA NOS		425	2	No	1	No	3	No	5	No	2

Investigator text for AEs encoded using MedDRA version xx.x.

(0) Grade: 1 = mild; 2 = moderate; 3 = severe; 4 = life threatening.

(1) Outcome: 1 = fatal; 2 = not recovered/not resolved;
3 = recovered/resolved; 4 = recovered/resolved with sequelae;
5 = recovering/resolving; 6 = unknown.

(2) Action taken with study drug: 1 = dose increased; 2 = dose not changed;
3 = dose reduced; 4 = drug interrupted; 5 = drug withdrawn; 6 = not
applicable; 7 = unknown.

AEL02_06: Listing of Adverse Events of Special Interest

Listing of Adverse Events of Special Interest: <Specify Patient Population with the Safety Evaluable Population as the default>

Protocol: xxnnnnn

Center/Patient ID	Adverse Event MedDRA Preferred Term	Age/Sex / Race	Study Day of Onset	AE Duration in Days	Most Serious	Grade (0)	Caused by Study Drug	Outcome (1)	Treatment for AE	Action Taken with Study Drug (2)
[REDACTED]	ANEMIA NOS		60	1	No	1	Yes	2	No	2
[REDACTED]	DIARRHEA NOS		425	2	No	1	No	3	No	2

Investigator text for AEs encoded using MedDRA version xx.x.

(0) Grade: 1 = mild; 2 = moderate; 3 = severe; 4 = life threatening.

(1) Outcome: 1 = fatal; 2 = not recovered/not resolved;

3 = recovered/resolved; 4 = recovered/resolved with sequelae;

5 = recovering/resolving; 6 = unknown.

(2) Action taken with study drug: 1 = dose increased; 2 = dose not changed;

3 = dose reduced; 4 = drug interrupted; 5 = drug withdrawn; 6 = not

applicable; 7 = unknown.

Study Period: 1 = before study entry 2 = During study 3 = Follow-up

AEL03_01: Listing of Serious Adverse Events

Listing of Serious Adverse Events: <Specify Patient Population with the Safety Evaluable Population as the default>

Protocol: xxnnnnn

Treatment: PLACEBO

Center/Patient ID SAE MedDRA Preferred Term	Age/Sex/Race	Study Day of Onset	AE Duration in Days	Most Extreme Grade (0)	Caused by Study Drug	Outcome (1)	Treatment for SAE	Action Taken with Study Drug (2)	Reason Classified as Serious (3)	Study Period (3)
[REDACTED]										
ANEMIA NOS		60	1	1	Yes	2	No	2	2	1
APPETITE DECREASED		91	2	2	No	3	No	3	3	2
[REDACTED]										
DIARRHEA NOS		425	2	1	No	3	No	2	6	2

Investigator text for AEs encoded using MedDRA version xx.x.

(0) Grade: 1 = mild; 2 = moderate; 3 = severe; 4 = life threatening.

Outcome: 1 = fatal; 2 = not recovered/not resolved; 3 = recovered/resolved; 4 = recovered/resolved with sequelae; 5 = recovering/resolving; 6 = unknown.

(1) Action taken with study drug: 1 = dose increased; 2 = dose not changed; 3 = dose reduced; 4 = drug interrupted; 5 = drug withdrawn; 6 = not applicable; 7 = unknown.

(2) Reason classified as serious: 1 = resulted in death; 2 = life threatening; 3 = required or prolonged in patient hospitalization; 4 = disabling; 5 = a congenital anomaly/birth defect in offspring of study subject; 6 = does not meet any of the above serious criteria, but may jeopardize the subject, and may require medical or surgical intervention to prevent one of the outcomes listed above

AET01_02: Safety Summary

Safety Summary: Safety Population
Protocol xxxnnnnn

	Group 1 (N=nnn)
Total number of patients with at least one AE	nn (xx.x%)
Total number of AEs	nn
Total number of patients with at least one	
AE with fatal outcome	nn (xx.x%)
Serious AE	nn (xx.x%)
AE leading to withdrawal from treatment	nn (xx.x%)
AE leading to dose modification/ interruption	nn (xx.x%)
Grade ≥3 AE	nn (xx.x%)
Related AE	nn (xx.x%)
Adverse events of special interest	
xxx	nn (xx.x%)
xxxxxx	nn (xx.x%)

.

Percentages are based on N in the column headings.
Multiple occurrences of the same AE in one individual are counted only once except for "Total number of AEs" row in which multiple occurrences of the same AE are counted separately.

Note: "Thrombotic microangiopathy" is based on the TMA definition in Point 5 of the Adverse Event of Special Interest section
All Adverse Events of Special Interest are identified using the rules defined in "Adverse Event of Special Interest" section..

AET02_01: Adverse Events by System Organ Class and Preferred Term

Adverse Events: <Specify Population>

Protocol: xxxnnnn

	Group1
	(N=xx)

ALL BODY SYSTEMS	
Total pts with any AE	xx (xx.x%)
Total number of AEs	xx
SOC 1	
Total pts with any AE	xx (xx.x%)
Preferred term 1	xx (xx.x%)
Preferred term 2	xx (xx.x%)
Preferred term 3	xx (xx.x%)
Preferred term 4	xx (xx.x%)
...	xx (xx.x%)
Total number of AEs	xx
SOC 2	
Total pts with any AE	xx (xx.x%)
Preferred term 1	xx (xx.x%)
Preferred term 2	xx (xx.x%)
Preferred term 3	xx (xx.x%)
Preferred term 4	xx (xx.x%)
...	xx (xx.x%)
Total number of AEs	xx

Investigator text for AEs encoded using MedDRA version xx.x. Percentages are based on N in the column headings.

For frequency counts by preferred term, multiple occurrences of the same AE in an individual are counted only once. For frequency counts of "Total number of events" rows, multiple occurrences of the same AE in an individual are counted separately.

AET04: Adverse Events by Highest NCI-CTCAE Grade

Adverse Events by Highest CTC Grade

Protocol: xxxnnnn

Population: xxx

MedDRA System Organ Class MedDRA Preferred Term	Grade (0)	Total (N=nnn ¹)
- Any adverse events -	- Any Grade -	nn ² (xx.x ³ %)
	1	nn ⁴ (xx.x%)
	2	nn (xx.x%)
	3	nn (xx.x%)
	4	nn (xx.x%)
	5	nn (xx.x%)
BLOOD AND LYMPHATIC SYSTEM DISORDERS		
- Overall -	- Any Grade -	nn ⁵ (xx.x%)
	1	nn ⁶ (xx.x%)
	2	nn (xx.x%)
	3	nn (xx.x%)
	4	nn (xx.x%)
	5	nn (xx.x%)
NEUTROPENIAS	- Any Grade -	nn ⁷ (xx.x%)
	1	nn ⁸ (xx.x%)
	2	nn (xx.x%)
	3	nn (xx.x%)
	4	nn (xx.x%)
	5	nn (xx.x%)

Investigator text for AEs encoded using MedDRA version xx.x. Percentages are based on N in the column headings.

All counts represent patients. Multiple occurrences of the same AE in one individual are counted once at the highest grade for this patient.

To the SOC Overall row counts, a patient contributes only with the AE occurring with the highest grade within the SOC.

(0) Grade: 1 = mild; 2 = moderate; 3 = severe; 4 = life threatening.

Similarly Summary of Adverse Events with NCI-CTCAE Grade >=3 table, Listing of Adverse Events with Most Severe NCI-CTCAE Grade >= 3 and Summary of Adverse Events Leading to Dose Interruption will be provided.

AET07_01 Adverse Events Resulting in Death

Adverse Events Resulting in Death: <Specify Population>

Protocol: xxnnnnn

Population: xxxx

MedDRA SOC and Preferred Term	Group 1 (N=nnn)
Total number of deaths	nn (xx.x%)
SOC1 / PT 1	nn (xx.x%)
SOC2 / PT 2	nn (xx.x%)
SOC3 / PT 3	nn (xx.x%)
SOC4 / PT 4	nn (xx.x%)
...	

Percentages are based on N in the column headings.

EUDRAT02 Serious Adverse Events, Fatal Serious Adverse Events, and Serious Adverse Events Related to Study Medication:

Serious Adverse Events, Fatal Serious Adverse Events, and Serious Adverse Events Related to Study Medication: <Analysis Population>
 Protocol: xxxnnnn

Group 1 (N=nnn)

MedDRA System Organ Class MedDRA Preferred Term	Patients (All)	Events (All)	Patients (Fatal)	Events (Fatal)	Events (Related)	Events (Fatal and Related)
Blood And Lymphatic System Disorders						
Anaemia	nnn	nnn	nnn	nnn	nnn	nnn
Coagulopathy	nnn	nnn	nnn	nnn	nnn	nnn
Febrile Neutropenia	nnn	nnn	nnn	nnn	nnn	nnn
Cardiac Disorders						
Acute Myocardial Infarction	nnn	nnn	nnn	nnn	nnn	nnn
Atrial Fibrillation	nnn	nnn	nnn	nnn	nnn	nnn
...						

NOTE: Number of events includes all occurrences.

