Appendix 9 Clinical Laboratory Tests

All study-required safety laboratory assessments will be performed by a local laboratory. Protocol-specific requirements for inclusion or exclusion of participants are detailed in Sections 5.1 and 5.2, respectively, of the protocol.

Additional tests may be performed at any time during the study as determined necessary by the Investigator or required by local regulations.

Table 1 Protocol-Required Safety Laboratory Assessments

Laboratory Assessments	Parameters
Hematology	CBC, including red blood cell count (RBC), hemoglobin, hematocrit, mean corpuscular volume (MCV), mean corpuscular hemoglobin concentration (MCH), mean corpuscular hemoglobin concentration (MCHC), platelet count, white blood cell count (WBC) with differential count (i.e., neutrophils, bands, lymphocytes, eosinophils, basophils, monocytes, and if present, blasts and other cells). Differential may be manual or automated, but must occur with each hematology assessment with emphasis on determination of the presence of peripheral blasts.
Clinical Chemistry ¹	Sodium, potassium, magnesium, chloride bicarbonate, calcium, phosphorus, albumin, total bilirubin, direct bilirubin, AST, ALT, ALP, LDH, creatinine, creatine kinase, blood urea nitrogen (BUN) or urea, uric acid, total protein, glucose, erythropoietin, iron.
Viral Serology	HIV (HIV-1/2 antibody), hepatitis B surface antigen (HBsAg), hepatitis C virus (HCV) antibody.
Pregnancy Test	All women of childbearing potential (including those who have had a tubal ligation) will have a blood pregnancy test at screening. Urine pregnancy tests will be performed at specified subsequent visits. If a urine pregnancy test is positive, it must be confirmed by a blood pregnancy test.
Urinalysis	Urinalysis (dipstick; pH, glucose, blood, protein, ketones and bilirubin). If there is a clinically significant positive result (confirmed by a positive repeated sample), urine will be sent to the laboratory for microscopy and culture. If there is an explanation for the positive dipstick results (e.g., menses), it should be recorded and there is no need to perform microscopy and culture. The results of each test must be entered into the CRF.

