6. APPENDICES

6.1 Definition of derivation for blood differentials

Each valid assessment of blood differentials with investigator units in percent must be converted to absolute value using the corresponding WBC assessment.

For a valid assessment of blood differential taken in percent the corresponding valid assessment of WBC must be located with matching date and time and must be used for conversion to absolute value. If there are multiple valid WBC assessments per given date and time, the assessment of WBC of the smallest result must be used.

Each valid assessment of banded or segmented neutrophils in absolute values must be converted into an assessment of total neutrophils by adding segmented and banded valid records of neutrophils of the same date and time.

If per the same date and time multiple valid records of banded neutrophils are present in the data, then for conversion into total neutrophils, only the smallest value is used. If only the valid record of segmented neutrophils is available for a specific date and time, then the value of banded neutrophils is considered to be zero. If only the valid record of banded neutrophils is available for specific date and time, then the value of segmented neutrophils is considered to be zero.

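### The SAP sets missing segmented neutrophils to zero, so a record with bands but no segmented count yields a total neutrophil count equal to the bands alone, which could distort the laboratory tables

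*SAP*

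**What the plan says.** SAP 5.8.4.2, item 2, gives the derivation: "Total Neutrophils are derived as the sum of segmented and band Neutrophils". It continues: "If one of the parameters is missing, it is assumed to be zero". The zero applies to either component. If several results fall within one time point, the latest is kept, and for exact ties: "If more than one result is at the same time, the smallest result is kept". The item ends with one exception: "In case the total neutrophils are reported together with the segmented and the bands, no calculation will be done, and the total neutrophils are used".

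SAP 6.1 states the same derivation as an obligation: "Each valid assessment of banded or segmented neutrophils in absolute values must be converted into an assessment of total neutrophils". For a date and time with a bands record and no segmented record, "then the value of segmented neutrophils is considered to be zero". Section 6.1 does not mention a reported total.

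Protocol Appendix 9 describes the required differential as "differential count (i.e., neutrophils, bands, lymphocytes, eosinophils, basophils, monocytes, and if present, blasts and other cells". Segmented neutrophils are not named there. The same appendix says that safety laboratory tests are done locally. The hematology table in SAP 6.2 carries total, band and segmented neutrophils as three separate tests.

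SAP 5.8.4.1 plans change-from-baseline tables and shift tables. The shift tables use all available data and the highest CTCAE grade after baseline.

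**The concern.** The two zero rules are not equivalent. Bands are usually a small part of the neutrophil count, so setting missing bands to zero changes the total little. Segmented cells are usually nearly all of it, so setting them to zero removes almost the whole count. The result is not an imputed neutrophil count but the band count under another name.

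Neutropenia is one of the drug's identified risks (Protocol 2.2.2 and 8.3.9), and Protocol 8.3.9.2 expects no significant fall in normal blood cells at the study doses. The neutrophil shift table is one place where that expectation is checked. Because it takes the worst post-baseline grade, a single false low value sets a patient's entry. In a single-arm cohort of about 20, one such patient is 1/20 = 5%, and there is no control arm to reveal an artefact. If the false value falls at baseline, a real on-treatment decline can be hidden.

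**Working it through.** The documents give no figure on this point, so there is nothing to reproduce. The check applies the written rule to each pattern a laboratory might report.

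**Rule, taken literally (SAP 5.8.4.2, item 2, all results from one draw):** if total, segmented and bands are all present, use the total. Otherwise derived = (segmented or 0) + (bands or 0), and the value kept is the minimum of the reported total (if any) and the derived value.

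**Proposed rule:** use the reported total if there is one; otherwise segmented + (bands or 0) if segmented is present; otherwise missing.

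**Example.** Assumed WBC 10 x10^9/L, 70% neutrophils and 3% bands, so total = 0.70 x 10 = 7.0, bands = 0.03 x 10 = 0.3 and segmented = 7.0 - 0.3 = 6.7.

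| Reported | SAP rule, literal | Proposed rule |
|---|---|---|
| total, segmented, bands | 7.0 | 7.0 |
| total, bands | min(7.0, 0 + 0.3) = 0.3 | 7.0 |
| total, segmented | min(7.0, 6.7 + 0) = 6.7 | 7.0 |
| segmented only | 6.7 | 6.7 |
| bands only | 0 + 0.3 = 0.3 | missing |

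The exception works where it applies. Missing bands cost 0.3; missing segmented cells cost 6.7.

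**Range for the total + bands pattern.** Assumed grid: WBC 4, 7, 10, 15, 20, 30 x10^9/L; neutrophils 70% of WBC; bands 0, 1, 3, 5, 10% of WBC. The true total then runs from 0.70 x 4 = 2.8 to 0.70 x 30 = 21.0. Under the literal rule the value kept always equals WBC x band fraction:

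| WBC | 0% | 1% | 3% | 5% | 10% |
|---|---|---|---|---|---|
| 4 | 0 | 0.04 | 0.12 | 0.20 | 0.40 |
| 7 | 0 | 0.07 | 0.21 | 0.35 | 0.70 |
| 10 | 0 | 0.10 | 0.30 | 0.50 | 1.0 |
| 15 | 0 | 0.15 | 0.45 | 0.75 | 1.5 |
| 20 | 0 | 0.20 | 0.60 | 1.0 | 2.0 |
| 30 | 0 | 0.30 | 0.90 | 1.5 | 3.0 |

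The ANC cut-offs in Protocol Table 8 serve here only as severity markers. Of 30 cells, 19 lie below 0.5 and 24 below 1.0 x10^9/L, although no true value is below 2.8. The value reaches 1.0 only when bands themselves do: WBC of at least 20 at 5% bands (1.0/0.05), or at least 10 at 10% (1.0/0.10). A value of exactly 0.50 is not in Table 8's lowest category, which is strictly below 0.5. Under the proposed rule all 30 cells return the reported total.

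**The case against.** Three arguments on the other side have weight.

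First, the SAP does not say that the reported total is used *only* when all three counts are present. The sentence shows an intention to prefer a reported total, and a programmer could apply it whenever a total exists. The smallest-result rule could likewise be ordinary duplicate handling; 6.1 uses the same convention for duplicate WBC and band records. On that reading the total + bands problem disappears. This stands as a possible reading, but the text does not require it, and 6.1 demands conversion with no exception. The bands-only case is unaffected by this argument, because its zero is stated outright.

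Second, nothing in the documents shows that any site reports bands without a segmented count. In Appendix 9, neutrophils listed beside bands may mean the segmented cells, in which case the sum is correct. SAP 5 also says that its specifications are not meant to cover rare data problems exhaustively. This stands: the pattern is plausible with local laboratories, but not demonstrated.

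Third, the reach is limited. A reader might infer that false severe neutropenia is bound to appear across the safety tables. The documents do not support that. Adverse event tables use investigator-reported events, investigators act on the laboratory's own results and not on an analysis variable, and no efficacy endpoint uses neutrophils. A laboratory with a constant format would also give a false low baseline, so the shift table need not show a new shift. Such a baseline would be conspicuous against the entry floor of 1.5 x10^9/L (Protocol 5.2, exclusion 7), and all laboratory data are listed.

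**Conclusion.** The rule is wrong as written for records with bands but no segmented or total count: the derived total equals the bands. Where total and bands are both reported, the text is ambiguous, and its literal reading replaces a correct total with the bands. Under the assumed differentials the error is large, for example 0.3 against 7.0 x10^9/L, with 24 of 30 grid cells falsely below 1.0.

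The consequence is conditional. False low values could enter the laboratory change-from-baseline table (LBT01), the shift table (LBSHIFT) and any listing that shows derived records, and true shifts could be masked where baseline is affected. Whether this happens depends on how the local laboratories report and how the exception is programmed. The number of affected records is unknown and may be zero. The WBC levels and cell percentages are assumptions, not trial data. Severity is moderate and confidence medium.

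**What to change.** Make the same change in SAP 5.8.4.2 (item 2) and SAP 6.1:

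1. A reported total neutrophil count always takes precedence over a derived one.
2. Derive total = segmented + bands only when segmented is present; missing bands may be taken as zero.
3. If segmented and total are both missing, set the total to missing.
4. Do not apply the smallest-result rule between a reported and a derived value; keep it for true duplicates of the same measurement.

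As a check, query any derived baseline below the 1.5 x10^9/L entry floor.

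The cost is a few sentences and program lines, with no change to trial conduct. The downside is that a few bands-only records become missing.
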